8.13 Dose Modifications for Pazopanib at Time of Retreatment

→ → Use the NCI Common Terminology Criteria for Adverse Events (CTCAE) version 4.0* unless otherwise specified ← ←			
CTCAE System/Organ/Class (SOC)	ADVERSE EVENT	AGENT	ACTION**
AT TIME OF RETREATMENT			
Investigations	Platelet count decreased Grade 3 or 4	Pazopanib	Hold until ≤ Grade 2 then restart at next lower dose level. If no recovery to grade 2, discontinue
Investigations	Electrocardiogram QT corrected interval prolonged ≥ 500msec Grade 3	Pazopanib	Discontinue pazopanib
Renal and urinary disorders	Creatinine > Grade 3	Pazopanib	Hold until < Grade 3 then restart at next lower dose level. If ≥ Grade 3 recurs, dose reduce again until no dose can be given

→ → Use the NCI Common Terminology Criteria for Adverse Events (CTCAE) version 4.0* unless otherwise specified ← ←			
CTCAE System/Organ/Class (SOC)	ADVERSE EVENT	AGENT	ACTION**
Vascular disorders	Thromboembolic event DVT/PE Grade 3 Grade 4 Arterial Thrombosis/Ischemia Any Grade	Pazopanib	Hold and initiate anticoagulant. Decrease 1 dose level if 
 • Subject must have been treated at desired level of anticoagulation for at least 1 week • No Grade 3 or 4 or clinically significant Grade 2, hemorrhagic events have occurred while on anticoagulation treatment. Note: When treating with warfarin, INR S/B monitored within 3 to 5 days after any change in pazopanib dosing and then at least weekly until INR is stable. The dose of warfarin may need to be adjusted to maintain the desired level of anticoagulation. Discontinue pazopanib Discontinue pazopanib
Vascular disorders	Hypertension	Pazopanib	See table 8.3
Gastrointestinal disorders	GI bleed Grade 2 Grade 3 or 4	Pazopanib	Interrupt pazopanib, restart at dose level 2 when bleeding has resolved and gradually titrate up as tolerated. Discontinue Pazopanib
Respiratory, thoracic and mediastinal disorders	Pulmonary bleed Grade 2 Grade 3 or 4	Pazopanib	Interrupt pazopanib, restart at dose level 2 when bleeding has resolved and gradually titrate up as tolerated. Discontinue Pazopanib

→ → Use the NCI Common Terminology Criteria for Adverse Events (CTCAE) version 4.0* unless otherwise specified ← ←			
CTCAE System/Organ/Class (SOC)	ADVERSE EVENT	AGENT	ACTION**
Dermatology/ Skin	Dermatitis Grade 2 skin changes w/pain, limiting ADL's Grade3 severe skin changes w/pain Limiting self-care ADL's	Pazopanib	Hold until ≤ 1, then restart at next lower dose level. If recurrent, reduce by another dose level or discontinue. Discontinue pazopanib
All others	Grade 2 or 3, if clinically significant Grade 4		Hold until ≤ Grade 1 Discontinue pazopanib

* Located at [REDACTED]

** Use the following to describe actions in the Action column:

- Omit = Treatment is not given for this cycle
- Hold/Delay = Treatment can be made up as part of this cycle
- Discontinue = Treatment is totally stopped

8.14 Guidelines for Management of Treatment Emergent Hepatotoxicity

Event	Dose Modification Algorithms
(A). ALT of $\leq 3.0 \times$ ULN	Continue pazopanib at current dose with full panel LFTs ^c monitored as per protocol.
(B). ALT $>3.0 \times$ ULN to $\leq 8.0 \times$ ULN without bilirubin elevation (defined as total bilirubin ⁰ $<2.0 \times$ ULN or direct bilirubin $\leq 35\%$) and without hypersensitivity symptoms (e.g., fever, rash)	
Liver Event Monitoring Criteria:
 
(1) Continue pazopanib at current dose levels.
 
(2) Monitor subject closely for clinical signs and symptoms; perform full panel LFTs^a weekly or more frequently if clinically indicated until ALT/AST is reduced to Grade 1.

(C). ALT $>8.0 \times$ ULN without bilirubin elevation (defined as total bilirubin ^b $<2.0 \times$ ULN or direct bilirubin $\leq 35\%$) and without hypersensitivity symptoms (e.g., fever, rash)	
1st occurrence – Liver Event Interruption Criteria^c:
 
(1) Interrupt pazopanib until toxicity resolves to \leqGrade 1 or baseline.
 
(2) Liver imaging and other laboratory investigations should be considered as clinically appropriate.
 
(3) Monitor subject closely for clinical signs and symptoms; perform full panel LFTs^a weekly or more frequently if clinically indicated until ALT/AST is reduced to Grade 1.
 
(4) Re-treatment may be considered if ALL following criteria are met:
 
 - ALT/AST reduced to Grade 1 - Total bilirubin $<1.5 \times$ ULN or direct bilirubin $\leq 35\%$ - No hypersensitivity signs or symptoms - Subject is benefiting from therapy. 
Recurrence – Liver Event Stopping Criteria^c:
 
Discontinue pazopanib permanently and monitor subject closely for clinical signs and symptoms; perform full panel LFTs^a weekly or more frequently if clinically indicated until ALT/AST is reduced to Grade 1.

(D). ALT $>3.0 \times$ ULN with concomitant elevation in bilirubin ⁰ (defined as total bilirubin $\geq 2.0 \times$ ULN; with direct bilirubin $>35\%$) or with hypersensitivity symptoms (e.g., fever, rash).	
Liver Event Stopping Criteria^c:
 
(1) Discontinue pazopanib immediately.
 
(2) Perform the following assessments to identify potential co-factors:
 
 - Eosinophil count - Viral serology for hepatitis A, B, C and E, cytomegalovirus, Epstein-Barr virus (IgM antibody, heterophile antibody, or monospot testing) - Anti-nuclear antibody, anti-smooth muscle antibody, Type 1 anti-liver kidney microsomal antibodies. - Serum creatinine phosphokinase for possible muscle injury caused LFT elevation - Liver imaging - Consider toxicological blood screen for possible contributing chemical/medical entities 
(3) Monitor subject closely for clinical signs and symptoms; record the appearance or worsening of clinical symptoms of hepatitis, or hypersensitivity, such as fatigue, nausea, vomiting, right upper quadrant pain or tenderness, fever rash or eosinophilia as relevant on the AE report form. Perform full panel LFTs^a weekly or more frequently if clinically indicated until LFTs are reduced to Grade 1.

Event	Dose Modification Algorithms
For isolated total bilirubin ⁰ elevation without concurrent ALT increases (defined as ALT <3 X ULN).	
(1) Isolated hyperbilirubinemia (i.e., in the absence of elevated ALT or other signs/symptoms of liver injury) does not require dose modification. Pazopanib inhibits UGT1A1 and OATP1B1, which can cause elevation of indirect (unconjugated) bilirubin in the absence of liver injury.
 
(2) If bilirubin is >1.5 x ULN in the absence of ALT elevation, fractionation of bilirubin elevation should be performed. If bilirubin is >35% direct (conjugated), further evaluation for underlying cause of cholestasis should be performed.

- a. Full panel LFTs include: AST, ALT, alkaline phosphatase, GGT, and total bilirubin. Coagulation tests should be performed as clinically indicated.
- b. Serum bilirubin fractionation should be performed if testing is available. If testing is unavailable and a subject meets the criterion of total bilirubin >1.5 x ULN, then the event should be promptly reported as an SAE.

Abbreviations: ALT alanine aminotransferase; AST aspartate aminotransferase; LFT liver function tests;; SAE serious adverse event; ULN upper limit of normal

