4.0 Test Schedule

Cycle length = 28 days.

Tests and procedures	Active Monitoring Cycle length = 28 days +/- 7 day window for study visits and tests. ⁵				
	≤21 days prior to randomization	Prior to each new cycle (≤7 days)	Prior to 3 rd and subsequent odd cycles (5, 7, 9, etc.)	At PD, withdrawal, removal, or end of protocol treatment	Observation (Clinical follow-up)
Informed Consent	X				
History and exam, wt., ECOG PS	X	X		X	X
Height	X				
Adverse event assessment	X	X ⁶		X	X
Echocardiogram (2D M-Mode)	X ⁸				
Hematology: CBC/ differential	X	X ⁵		X	X
Chemistry: SGOT (AST), alk phos, T. bili, creatinine, calcium, phos, glucose, Na, K, ALT, GFR, LDH ¹¹	X	X ^{4,5}		X	X
G6PD test	X ^{R, 9}				
Urinalysis	X			X	
Thyroid function test (TSH)	X		X		
Coagulation test: INR, APTT	X				
Tumor measurement	X ¹		X ¹		X ^{1, 10}
CT/MRI brain, if needed (See Section 3.29a)	X		X		
Bone scan ¹²	X		X		
ECG	X		X		
Pregnancy test (serum)	X ²				
Mandatory archival tissue collection (see Section 17.2)	X ^{R, 7}				
Patient Medication Diary (Appendix II)		X ³		X ³	

¹ CT chest, abdomen, and pelvis with IV contrast. If unable to receive IV contrast, MRI abdomen/pelvis with contrast and CT chest without contrast are acceptable. Use same imaging method throughout the study.

- ² For individuals of childbearing potential only. Must be done ≤ 7 days prior to randomization.
- ³ The diary must begin the day the patient starts taking the medication and must be completed per protocol and returned to the treating institution every 4 weeks.
- ⁴ For ARM- A (ascorbic acid group) only: Draw at baseline then weekly for Cycle 1, then for subsequent cycles on Day 14 and Day 28. For ARM B only: draw at baseline then once every cycle.
- ⁵ Labs do not have to be repeated prior to Cycle 1 if they were done ≤ 5 days prior to cycle.
- ⁶ Starting with Cycle 2, AE's for Cycle 1 are assessed prior to the beginning of Cycle 2 and are recorded under Cycle 1 AE, following this format for all subsequent cycles.
- ⁷ Receipt of archival tumor tissue (if available) is not required for study randomization and initiation of therapy. . However, it is mandatory to receive the required tissue ≤ 30 days from registration.
- ⁸ Echocardiogram done ≤ 6 months prior to randomization is acceptable.

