10.3 Assessment of Attribution

When assessing whether an adverse event is related to a medical treatment or procedure, the following attribution categories are utilized:

- Definite - The adverse event *is clearly related* to the agent(s).
- Probable - The adverse event *is likely related* to the agent(s).
- Possible - The adverse event *may be related* to the agent(s).
- Unlikely - The adverse event *is doubtfully related* to the agent(s).
- Unrelated - The adverse event *is clearly NOT related* to the agent(s).

Events determined to be possibly, probably or definitely attributed to a medical treatment suggest there is evidence to indicate a causal relationship between the drug/device and the adverse event.

10.4 Expedited Reporting Requirements for Studies using Commercial Agent(s) ONLY:

Expedited Reporting Requirements for Adverse Events that Occur in a Non-IND/IDE trial within 30 Days of the Last Administration of a Commercial Agent^{1,2}**FDA REPORTING REQUIREMENTS FOR SERIOUS ADVERSE EVENTS (21 CFR Part 312)**

NOTE: Investigators **MUST** immediately report to the sponsor **ANY** Serious Adverse Events, whether or not they are considered related to the investigational agent(s)/intervention (21 CFR 312.64)

An adverse event is considered serious if it results in **ANY** of the following outcomes:

- 1) Death
- 2) A life-threatening adverse event
- 3) An adverse event that results in inpatient hospitalization or prolongation of existing hospitalization for \geq 24 hours
- 4) A persistent or significant incapacity or substantial disruption of the ability to conduct normal life functions
- 5) A congenital anomaly/birth defect.
- 6) Important Medical Events (IME) that may not result in death, be life threatening, or require hospitalization may be considered serious when, based upon medical judgment, they may jeopardize the patient or subject and may require medical or surgical intervention to prevent one of the outcomes listed in this definition. (FDA, 21 CFR 312.32; ICH E2A and ICH E6).

ALL SERIOUS adverse events that meet the above criteria **MUST** be immediately reported to the sponsor within the timeframes detailed in the table below.

Hospitalization	Grade 1 Timeframes	Grade 2 Timeframes	Grade 3 Timeframes	Grade 4 & 5 Timeframes
Resulting in Hospitalization \geq 24 hrs	7 Calendar Days			24-Hour 3 Calendar Days
Not resulting in Hospitalization \geq 24 hrs	Not required		7 Calendar Days	

Expedited AE reporting timelines are defined as:

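### At ALT above 3 × ULN with total bilirubin of 2 × ULN or more, 8.14 cannot assign a pazopanib action when the direct fraction is unavailable, and 15.198 gives a different rule

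*Combined protocol and SAP*

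**What the plan says.** The table in Section 8.14 sorts liver events by ALT, total bilirubin, direct bilirubin fraction and hypersensitivity symptoms.

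- Row A (ALT up to 3 × ULN): continue.
- Row B (ALT above 3 and up to 8 × ULN) and row C (ALT above 8 × ULN) both require no bilirubin elevation, defined as total bilirubin below 2.0 × ULN or a direct fraction of at most 35%, and no hypersensitivity symptoms. Row B continues pazopanib. Row C interrupts it at a first occurrence and stops it permanently at a recurrence.
- Row D covers ALT above 3 × ULN "with concomitant elevation in bilirubin", defined as total bilirubin of at least 2.0 × ULN with a direct fraction above 35%, or ALT above 3 × ULN with hypersensitivity symptoms. It discontinues pazopanib.
- The isolated-bilirubin row (ALT below 3 × ULN) states: "Isolated hyperbilirubinemia (i.e., in the absence of elevated ALT or other signs/symptoms of liver injury) does not require dose modification". It asks for fractionation above 1.5 × ULN.

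On the inputs, footnote a reads "Full panel LFTs include: AST, ALT, alkaline phosphatase, GGT, and total bilirubin". The chemistry line in Section 4.0 begins "Chemistry: SGOT (AST), alk phos, T. bili, creatinine" and nowhere lists a direct fraction. Footnote b asks for fractionation where the test can be had and then turns to SAE reporting: "If testing is unavailable and a subject meets the criterion of total bilirubin >1.5 x ULN, then the event should be promptly reported". It names no dosing action and sets no ALT condition.

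Section 15.198, in the nursing guidelines for pazopanib, calls for permanent discontinuation when AST/ALT is above 3 × ULN and bilirubin is above 2 × ULN. A second sentence allows weekly monitoring on treatment for mild hyperbilirubinemia with suspected or known Gilbert's syndrome. Section 16.11 counts going off protocol treatment for an adverse event as treatment failure.

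**The concern.** A stopping rule should return one answer for every patient whose ALT and bilirubin are known. Here the answer can depend on a third measurement that the protocol itself expects some sites not to have, and the footnote written for that situation says how to report the event but not what to do with the drug. A second section gives an instruction that does not match the table.

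The case affected is not remote. Transaminases and bilirubin rising together is the picture in the boxed warning reproduced in 15.17. It also touches the primary endpoint. If one site stops pazopanib for such an event and another continues, the first patient is a TFF40 failure on that ground and the second is not, for the same laboratory values. Section 4.0 has chemistry drawn more often in Arm A than in Arm B, so the two arms could meet the ambiguity at different rates.

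**Working it through.** The plan states no figure to reproduce here, and the question is whether the decision table is complete. Each row was evaluated as true, false or undetermined over a grid of values.

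Definitions, from 8.14, with T = total bilirubin (× ULN) and d = direct fraction:

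- Not elevated (rows B and C): T < 2.0 or d ≤ 35%.
- Elevated (row D): T ≥ 2.0 and d > 35%.

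These two definitions are exact complements, which supports reading row D as needing both conditions. When T < 2.0, the first is true whatever d is. When T ≥ 2.0, each reduces to a statement about d alone, so an unknown d leaves both undetermined.

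Results without hypersensitivity symptoms. The 15.198 column is its main instruction (AST/ALT > 3, bilirubin > 2). The last column is footnote b's report (fraction unavailable, T > 1.5).

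| ALT (× ULN) | T (× ULN) | d | 8.14 row | 15.198 says discontinue | Footnote b SAE report |
|---|---|---|---|---|---|
| 5 | 1.7 | unavailable | B | no | yes |
| 5 | 2.0 | unavailable | B or D, undetermined | no | yes |
| 5 | 2.5 | unavailable | B or D, undetermined | yes | yes |
| 5 | 2.5 | 20% | B | yes | no |
| 5 | 2.5 | 50% | D | yes | no |
| 10 | 1.7 | unavailable | C | no | yes |
| 10 | 2.0 | unavailable | C or D, undetermined | no | yes |
| 10 | 2.5 | unavailable | C or D, undetermined | yes | yes |
| 10 | 2.5 | 20% | C | yes | no |
| 10 | 2.5 | 50% | D | yes | no |

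With hypersensitivity symptoms, row D is true at every point of the grid and the fraction is not needed.

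Three things follow.

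1. **Gap.** With T ≥ 2.0, no fraction and no hypersensitivity symptoms, 8.14 leaves open continue versus discontinue (ALT above 3 and up to 8) or interrupt versus discontinue (ALT above 8, first occurrence). At a recurrence with ALT above 8, rows C and D both stop the drug, so the gap does not matter there.
2. **Conflict.** At T = 2.5 and d = 20%, 8.14 returns row B (continue) or row C (interrupt at a first occurrence), while 15.198 says to stop permanently. The fraction is known in this case, so the conflict is separate from the gap.
3. **Boundary.** At T exactly 2.0, 15.198 does not apply because its limit is strict, whereas row D's limit includes 2.0.

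For scale on the endpoint: with 41 patients per arm (16.21), one patient counted as a failure rather than a success moves that arm's TFF40 by 1/41 = 2.4 percentage points, if the patient would otherwise have been failure-free at 40 weeks. The documents do not allow an estimate of how many such patients there would be.

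**The case against.** The strongest objection is that the protocol does act on this case. A reader of 8.14 alone might infer that the plan is silent and leaves the decision to the site. The documents do not support that: 15.198 is protocol text, gives a drug action and needs no fraction. The generic last row of the 8.12 table, which works by grade, could also be read as a fallback. What remains is that 8.14 points to neither, and that 15.198 disagrees with rows B and C. The Gilbert's sentence in 15.198 may soften that disagreement for some patients with mainly indirect bilirubin, but it is tied to that diagnosis and does not define mild.

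A reader might also infer that every row turns on the fraction once bilirubin reaches 2.0 × ULN. It does not. Row D applies on hypersensitivity symptoms alone, and row A and the isolated-bilirubin row's dosing statement need no fraction.

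Nor does the absence of direct bilirubin from Section 4.0 show that the test was overlooked. It is a triggered test, and 8.14 requests it. The difficulty is confined to sites where it cannot be done.

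Finally, a reader might infer that footnote b over-reports a benign finding. The text does not show this. The table links pazopanib's transporter and enzyme effects only to indirect bilirubin, so an unfractionated rise cannot be called benign. The 1.5 × ULN level is where the same table asks for fractionation. In 10.4, where "An adverse event is considered serious if it results in" any of six outcomes, the sixth is left to medical judgment. No planned analysis uses SAE counts: 16.325 works with maximum grades and grade 3 or higher events, and 16.42 with grades 4 and 5. What stands is only that the footnote does not say whether its trigger is meant to apply whatever the ALT.

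**Conclusion.** The point holds in a limited form. For patients without hypersensitivity symptoms who have ALT above 3 × ULN and total bilirubin of 2.0 × ULN or more, 8.14 cannot assign a row when the direct fraction is unavailable. Where 15.198 reaches the same patients, it contradicts rows B and C if the fraction is known to be 35% or less. Sites thus have a rule that is either indeterminate or in conflict with another section, in a safety decision that also feeds TFF40.

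The effect on the endpoint cannot be sized, because the documents give neither the frequency of these events nor the share of sites without fractionation. Nothing here bears on the sample size or the planned comparison.

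The conclusion rests on two readings of the text as extracted. First, the superscript on bilirubin in rows B and D, which prints as a zero, is taken as b. Second, the interruption and stopping criteria carry a superscript c whose note does not appear in the available text. If that note exists and covers an unknown fraction, the gap would close. It would leave the conflict with 15.198 unless it addressed that as well.

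**What to change.** Reconcile 8.14 rows B to D, footnote b and 15.198 so that every combination of ALT and bilirubin, including an unknown direct fraction and a bilirubin of exactly 2.0 × ULN, leads to one pazopanib action, and cross-refer the two sections. Row C's re-treatment criteria rest on the same fraction (total below 1.5 × ULN or direct at most 35%) and belong in the same edit. Which action applies is a clinical decision for the sponsor.

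In that edit, state whether footnote b's SAE report above 1.5 × ULN applies regardless of ALT, and how it relates to the seriousness criteria in 10.4.

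A reflex direct bilirubin entry in Section 4.0 is optional. 8.14 already requests the test, and an entry would not help where the test cannot be done.

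The cost is a few lines of wording in the next amendment and a notice to sites. No analysis, sample size or visit changes.

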8.2 Dose Modifications for IV Ascorbic Acid at Time of Treatment

→ → Use the NCI Common Terminology Criteria for Adverse Events (CTCAE) version 4.0* unless otherwise specified ←			
CTCAE System/Organ/Class (SOC)	ADVERSE EVENT	AGENT	ACTION**
DAY OF TREATMENT ADVERSE EVENT			
Renal and Urinary disorders	Renal Function	Ascorbic Acid	SEE TABLE IMMEDIATELY BELOW(section 8.21)
General Disorders and Administration Site Conditions	Dizziness during Infusion Grade 1 (mild) -3 (severe) Grade 1 = mild unsteadiness or sensation of movement Grade 2 = Moderate unsteadiness or sensation of movement limiting instrumental ADL Grade 3 Severe	Ascorbic Acid	Stop infusion until dizziness resolves (about 10-15 min), restart at half the infusion rate when dizziness has resolved, and gradually increase as tolerated. If dizziness re-occurs then repeat above instructions.
Respiratory, Thoracic and Mediastinal Disorders	Bronchopulmonary hemorrhage Grade 1 Grade 2-4	Ascorbic Acid	No dose adjustment required Hold until resolution to grade 1
Vascular Disorders	→Hypotension Grade 2 Grade 3 Grade 4 →Hemorrhage (any organ) Grade 1 Grade 2-4	Ascorbic Acid	No dosage adjustment required Cut dose by 50% Hold until improvement to Grade 3 No dose adjustment required Hold until resolution to grade 1
Gastrointestinal Disorders	→Gastrointestinal symptoms (Nausea, vomiting, or diarrhea) Grade 2-3 Grade 4	Ascorbic Acid	Antiemetics and antidiarrheals can be used and should be used prior to reducing dose. If they are ineffective then reduce dose by 50%. Provision to gradually increase (at next infusion day) back to target dose as tolerated at treating physician judgment Hold until resolution to grade 3 or below

→ → Use the NCI Common Terminology Criteria for Adverse Events (CTCAE) version 4.0* unless otherwise specified ←			
←			
CTCAE System/Organ/Class (SOC)	ADVERSE EVENT	AGENT	ACTION**
Hepatobiliary Disorders	→Hepatobiliary disorders Other, specify Grade 2-3 Grade 4	Ascorbic acid	No dose adjustment necessary Cut dose by 50%

* Located at [REDACTED]

** Use the following to describe actions in the Action column:

- Omit = Treatment is not given for this cycle
- Hold/Delay = Treatment can be made up as part of this cycle
- Discontinue = Treatment is totally stopped

8.21 Dose modifications for IV Ascorbic Acid based on Renal function

Increase from baseline serum creatinine	Creatinine < 2.0 mg/dL	Creatinine ≥ 2.0 mg/dL
< 50%	
 • Continue treatment. • No dose reduction. 	
 • Hold dose. • Ensure adequate hydration. • Resume when creatinine < 2.0 mg/dL.
50% (1.5 times)	
 • Ensure adequate hydration. • For first occurrence only: 
 ○ Administer 50% of the previous dose. ○ Increase the next scheduled dose to 75%, then to 100% as long as creatinine remains < 2 times baseline. ○ Continue at the highest dose tolerated. 	
60% (1.6 times)		
70% (1.7 times)		
80% (1.8 times)		
90% (1.9 times)		
≥ 100% (≥2 times)	
 • Hold dose. • Ensure adequate hydration. • Resume when creatinine < 2 times baseline. 	
 • Hold dose. • Ensure adequate hydration. • Resume when creatinine < 2.0 mg/dL and < 2 times baseline.

